Numerator: Number of post-stroke patients with one or more of these post-stroke complications during hospitalization

Denominator: Total number of post-stroke patients

Indicator 18

Proportion of patients given a carotid Doppler test within 24 hours

Numerator: Number of post-stroke patients given a carotid Doppler test within 24 hours

Denominator: Total number of post-stroke patients

Effectiveness

Indicator 19

Proportion of patients who die from stroke in hospital within 7 days and within 30 days following admission

Numerator 1: Number of patients who die from stroke within 7 days following admission to hospital

Numerator 2: Number of patients who die from stroke within 30 days following admission to hospital

Denominator: Total number of ischemic stroke patients hospitalized or discharged from hospital

Indicator 20

Proportion of patients with severe disability at discharge (mRS 0-3) (Calculate proportion of patients for each modified Rankin score, mRS of 1 to 5.)

Numerator: Number of patients with a modified Rankin score (mRS) between 0 and 3 at discharge

Denominator: Total number of patients with a modified Rankin score recorded at discharge

Indicator 21

Proportion of patients with increased shoulder pain based on pain intensity score evaluated with a valid tool using reference data during hospitalization

Numerator: Number of post-stroke patients with increased shoulder pain based on pain intensity score evaluated with a valid tool

Denominator: Number of post-stroke patients with shoulder pain

Indicator 22

Proportion of patients readmitted to short-term hospital care for a stroke-related issue after discharge (post 30 days)

Numerator: Number of patients readmitted to short-term hospital care for a stroke-related issue within 30 days after discharge

Denominator: Total number of post-stroke patients re-hospitalized after discharge

Continuity

Indicator 23

Proportion of post-stroke patients prescribed an anticoagulant, lipid-lowering medication, an antiplatelet, an antihypertensive, or a hypoglycemic at discharge (Result per medication)

Numerator: Number of post-stroke patients prescribed an anticoagulant, lipid-lowering medication, an antiplatelet, an antihypertensive, or a hypoglycemic at discharge

Denominator: Total number of post-stroke patients prescribed one or more medications

Indicator 24

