H2. Date and time of death DD/MM/YYYY ____ / ____ / ____ HH: MIN ____ : ____
H3. Short stay discharge  1-No  2-Yes  3-Not applicable  99-Missing data
H4. Date and time of short stay discharge DD/MM/YYYY ____ / ____ / ____ HH: MIN ____ : ____
H5. Date and time of stroke unit discharge

DD/MM/YYYY ____ / ____ / ____ HH: MIN ____ : ____	
H6. Date and time of intensive care unit discharge DD/MM/YYYY ____ / ____ / ____ HH: MIN ____ : ____	
H7. Presence in the record of functional independence evaluation using modified Rankin Scale (mRS)  1-No  2-Yes  3-Not applicable  99-Missing data	
H8. Clinician performing the functional independence evaluation using modified Rankin Scale (mRS) in the record  1-Nurse  2-Neurologist  3-Occupational therapist  4-Other: _____  99-Missing data	
H9. mRS result at discharge: _____	
H10. Anticoagulant prescribed at discharge  1-No  2-Yes  3-Not applicable  99-Missing data	
H11. Lipid-lowering medication prescribed at discharge  1-No  2-Yes  3-Not applicable  99-Missing data	
H12. Antiplatelet prescribed at discharge  1-No  2-Yes  3-Not applicable  99-Missing data	
H13. Hypertensive prescribed at discharge  1-No  2-Yes  3-Not applicable  99-Missing data	
H14. Hypoglycemic prescribed at discharge  1-No  2-Yes  3-Not applicable  99-Missing data	
H15. Discussion with patient about targeted goals for discharge  1-No  2-Yes  3-Not applicable  99-Missing data	
H16. Individualized intervention plan developed with patient and caregivers  1-No  2-Yes  3- Not applicable  99-Missing data	

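### Indicator 20 (mRS at discharge) contradicts itself on label and score range, and its denominator makes the 0 to 3 share conditional on survival and charting

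*Protocol*

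**What the plan says.** Protocol, Appendix 1, Effectiveness, Indicator 20 has four parts:

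- Label: "Proportion of patients with severe disability at discharge (mRS 0-3" (the bracket closes after the range).
- Denominator, restricted to charted patients: "Total number of patients with a modified Rankin score recorded at discharge".
- Numerator, which takes in score 0: "Number of patients with a modified Rankin score (mRS) between 0 and 3 at discharge".
- Score-by-score breakdown, which starts at 1: "Calculate proportion of patients for each modified Rankin score, mRS of 1 to 5".

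Indicator 19, directly above it, covers mortality: "Proportion of patients who die from stroke in hospital within 7 days and within 30 days following admission". Its denominator is all ischemic stroke patients hospitalized or discharged.

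In Appendix 2, section H, death is its own item (H1). H7 asks for "Presence in the record of functional independence evaluation using modified Rankin Scale (mRS" and offers a not-applicable option. "H9. mRS result at discharge" is a blank field with no stated range. No rule says what H7 or H9 should hold for a patient who died.

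Section 3.5 describes the indicators for each centre and for all three together. It makes them dependent variables in regressions where there are enough data.

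**The concern.** Three features of one definition do not fit together.

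1. The label names severe disability, but the range counted is 0 to 3. The Protocol does not spell out the scale. On its ordinary convention higher scores are worse, so label and numerator point in opposite directions.
2. Score 0 is in the numerator and, when recorded, in the denominator, but it has no line in the breakdown.
3. The denominator is restricted to recorded discharge scores. A patient who dies in hospital would normally have none, and a patient whose score was not charted has none by definition.

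At stake is what a per-centre figure means. It would describe function among charted survivors, and its value would also reflect who survived and who was scored. Hypothesis 2 (section 2) concerns similarities and differences between types of centre, and section 8 promises to highlight the best and worst results, so the figures will be read side by side. A regression on this indicator would carry the same conditioning.

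**Working it through.** The Protocol gives no mRS distribution, mortality or charting rate, so there is no figure of the plan's own to reproduce. The percentages below are illustrations on assumed values. The record counts of 75 and 45 are the expected tertiary and secondary samples in section 3.3.2.

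**Breakdown against numerator.** If a share s of scored patients has mRS 0, the listed categories 1 to 5 add to 1 − s. For s between 5% and 20% (assumed) the listed total is 95% to 80%.

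**Deaths, constant function in survivors.** Let q be the 0 to 3 share among survivors and m the in-hospital mortality. With every survivor scored and deaths unscored, Indicator 20 equals q, and the share of all patients is q × (1 − m). With q = 60% (assumed):

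| m (assumed) | Indicator 20 | Share of all patients |
|---|---|---|
| 5% | 60% | 0.60 × 0.95 = 57% |
| 10% | 60% | 0.60 × 0.90 = 54% |
| 15% | 60% | 0.60 × 0.85 = 51% |

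The largest gap is 60 − 51 = 9 points.

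**Deaths, constant number at 0 to 3.** Take N = 75 with 38 patients at 0 to 3 (assumed). The share of all patients is 38/75 = 50.7% whatever the number of deaths. Indicator 20 is 38/(75 − deaths):

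- 0 deaths: 38/75 = 50.7%
- 4 deaths: 38/71 = 53.5%
- 8 deaths: 38/67 = 56.7%
- 11 deaths: 38/64 = 59.4%
- 15 deaths: 38/60 = 63.3%

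For N = 45 with 22 at 0 to 3 (assumed), the share of all is 22/45 = 48.9%. With 9 deaths Indicator 20 is 22/36 = 61.1%.

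**Charting.** Take 68 survivors of 75, of whom 38 are at 0 to 3 and 30 at 4 to 5 (assumed). With charting rates a and b in the two groups, Indicator 20 is 38a/(38a + 30b):

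- a = b = 1: 38/68 = 55.9%
- a = b = 0.7: 26.6/47.6 = 55.9%
- a = 0.9, b = 0.5: 34.2/49.2 = 69.5%
- a = 0.5, b = 0.9: 19/46 = 41.3%

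Equal under-charting does no harm. Outcome-dependent charting moves the result either way.

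**Which denominator to put beside it.** In the same example, at 70% charting in both groups:

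- All 75 sampled patients: 26.6/75 = 35.5%, against 50.7% with full charting. This ties the share directly to charting.
- Known outcome (scored survivors plus the 7 deaths): 26.6/(47.6 + 7) = 48.7%, against 50.7%. This is much less sensitive. It still falls slightly, because a death is always known and a score is not.

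**The case against.** The strongest reply is that little is lost. Score 0 is in the headline proportion, and only the supplementary breakdown leaves it out. If deaths carry no score, the recorded scores run from 0 to 5 over one denominator. The headline is then 1 − p4 − p5 and the share at 0 is 1 minus the sum of p1 to p5, so both can be recovered. A reader might infer that the indicator discards score 0 altogether or that the breakdown cannot rebuild the headline. The text does not support either.

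Deaths also have their own indicator, and keeping survival and function apart is a legitimate design. This stands in part. Indicator 19 counts only deaths from stroke within 30 days, over a different denominator. A death from another cause, or in hospital after day 30, appears in neither indicator. Nor is it certain that deaths are excluded: H9 has no stated range, so a collector could enter 6. Exclusion is the natural reading, but the definition leaves it open.

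A reader might also infer that a centre with more deaths or fewer charted scores will look better. The documents do not support that as a general statement. Fewer scores bias the share only when charting depends on outcome, and then in either direction. A higher 0 to 3 share looks better only if 0 to 3 is read as the good outcome; under the printed label it looks worse.

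Finally, section 3.1 asks each centre to compare with itself, Objective 1 is descriptive, and section 8.2 acknowledges missing data. These points limit the consequence. They do not remove the contradiction in the definition or stop per-centre figures being set side by side.

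**Conclusion.** The point holds in this form. Indicator 20 is inconsistent between label and numerator and between numerator and breakdown, and both show on the face of the text. Its denominator makes the 0 to 3 share conditional on charting and, on the natural reading, on survival. Under the assumptions above, the survival part amounts to 3 to 9 points at 5% to 15% in-hospital mortality with 60% of survivors at 0 to 3. The charting part is zero when charting is unrelated to outcome; otherwise it can be large in either direction.

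This is one of 29 indicators, and neither the sample size nor any named test rests on it. It should be corrected because the definition cannot be applied consistently as printed and the correction is nearly free. It does not call the study's design into question.

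**What to change.** - Reconcile the label with the numerator, so that the named outcome and the counted scores are the same thing.
- Per centre and overall, report mRS 0, 1, 2, 3, 4, 5, death (from H1) and not recorded (from H7) as separate categories over all sampled patients, adding to 100%.
- Give the 0 to 3 proportion twice: among patients with a known outcome, with deaths counted as not 0 to 3, and, as now, among those with a recorded score. Do not make all sampled patients its only denominator.
- State the permitted range of H9, and say that death is taken from H1. A death coded as not applicable in H7 is then not counted as an uncharted score.

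H1, H7 and H9 are already collected, so no new data are needed. The cost is a few lines in Appendices 1 and 2, one larger table, and a somewhat lower 0 to 3 proportion where deaths are counted.

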8.2 Limitations

The study's main limitation involves the level of data collection in the health records of different hospitals whose different and separate databases complicate the research. Additionally, retrospective research has certain limitations including the possibility of missing data during measurement of indicators or data that vary depending on the quality of notes in the records, factors the researcher cannot control for. What's more, input errors may occur during data collection. To limit this type of error during data collection in health records, an automated coding system will be inserted in the file with a drop-down menu to enter textual data. A validation system will be integrated to issue an error message if aberrant data are recorded. As well, a data validation will be regularly performed to ensure the quality of the data collected by the research assistant. Although the number of indicators to measure ensures good representativity of acute patient management, priority indicators must be chosen to make data collection feasible within the context of a doctoral study. Additionally, certain hospital characteristics must be collected through observation and consultations with various available on-site stakeholders given the lack of written documentation on the subject in the different centers. Finally, the association between

determinants and results will not explain the cause of the different results, but will further identify the elements likely to influence the results obtained.

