F11. Neurological evaluation by a nurse using the Glasgow Coma Scale post revascularization treatment

1-No 2-Yes 3-Not applicable 99-Missing data

F12. Result of Glasgow Coma Scale post revascularization treatment: _____

F13. Shoulder pain evaluation by the physiotherapist

1-No 2-Yes 3-Not applicable 99-Missing data

F14. Presence of shoulder pain

1-No 2-Yes 3-Not applicable 99-Missing data

F15. Result of first shoulder pain evaluation: _____

F16. Shoulder pain re-evaluation by physiotherapist

1-No 2-Yes 3-Not applicable 99-Missing data

F17. Result of second shoulder pain evaluation: _____

G. Complications during hospitalization

G1. Intracranial hemorrhage  1-No  2-Yes  99-Missing data	G2. Urinary tract infection  1-No  2-Yes  99-Missing data
G3. Aspiration pneumonia  1-No  2-Yes  99-Missing data	G4. Other pneumonia (nosocomial, ventilator-associated, etc.) Specify: _____  1-No  2-Yes  99-Missing data
G5. Malnourishment  1-No  2-Yes  99-Missing	G6. Convulsions  1-No  2-Yes  99-Missing data
G7. Deep vein thrombophlebitis  1-No  2-Yes  99-Missing data	G8. Depression  1-No  2-Yes  99-Missing data
G9. Temperature increase  1-No  2-Yes  99-Missing data	G10. Anxiety  1-No  2-Yes  99-Missing data
G11. Pulmonary embolism  1-No  2-Yes  99-Missing data	G12. Gastrointestinal bleeding  1-No  2-Yes  99-Missing data
G13. Shoulder subdislocation  1-No  2-Yes  99-Missing data	G14. Contracture  1-No  2-Yes  99-Missing data

H. Discharge / Transfer

H1. Death  1-No  2-Yes  99-Missing data

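### Indicator 21 counts increases in shoulder pain over all patients with shoulder pain, including those without two scores, so the result is diluted by incomplete re-evaluation

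*Protocol*

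**What the plan says.** Appendix 1 of the protocol, under Effectiveness, defines Indicator 21 as "Proportion of patients with increased shoulder pain based on pain intensity score evaluated with a valid tool using reference data during hospitalization". It then fixes both parts of the fraction. The upper part is "Numerator: Number of post-stroke patients with increased shoulder pain based on pain intensity score evaluated with a valid tool". The lower part, which makes no mention of any score, is "Denominator: Number of post-stroke patients with shoulder pain".

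Appendix 2, section F, collects the data as separate items: "F14. Presence of shoulder pain", the first score (F15), "F16. Shoulder pain re-evaluation by physiotherapist" and "F17. Result of second shoulder pain evaluation". F16 can be answered no, yes, not applicable or missing.

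Indicator 20, directly above in Appendix 1, also depends on a recorded score and handles it differently: "Denominator: Total number of patients with a modified Rankin score recorded at discharge".

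Section 8.2 expects "the possibility of missing data during measurement of indicators or data that vary depending on the quality of notes in the records", but gives no rule for this indicator. Section 3.5 reports proportions for each centre and for all three together. Section 8 plans to highlight the highest- and lowest-performing results.

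**The concern.** The numerator needs two scores and the denominator needs none. A patient recorded as having shoulder pain (F14 = yes) but not re-evaluated (F16 = no) is counted below the line and can never be counted above it. The same holds for a patient with pain whose first score was not recorded. Such patients have the same effect on the proportion as patients whose pain was scored twice and did not rise.

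A lower value is the better result here, so gaps in follow-up improve the figure. Two centres with the same course of pain can report different values because one repeats the score more often. Comparing a centre only with itself does not avoid this, because its own value is diluted by its own re-evaluation rate.

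**Working it through.** The protocol states no expected value for Indicator 21, so there is no figure to reproduce. The check follows from the definition.

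**Inputs**
- Numerator: patients with F17 greater than F15 (Appendix 1 for the definition, Appendix 2 section F for the items).
- Denominator: patients with F14 = yes (same sources).
- r, the share of shoulder-pain patients with both scores: not in the documents, assumed 20% to 100%.
- p, the rate of increase: not in the documents, assumed 20% to 40%.

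**Formula.** If re-evaluation is unrelated to change, the indicator as written equals r × p. With the denominator limited to patients who have both scores, it equals p.

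| p | r = 100% | r = 50% | r = 20% | r = 0% |
|---|---|---|---|---|
| 20% | 20% | 10% | 4% | 0% |
| 30% | 30% | 15% | 6% | 0% |
| 40% | 40% | 20% | 8% | 0% |

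The last column needs no assumption about p: with no second scores, the numerator is empty.

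**Two centres with the same rate among those scored twice (assumed counts).** Each has 20 patients with shoulder pain. Centre A scores 18 of them twice and 6 rise; centre B scores 6 twice and 2 rise.
- As written: A 6/20 = 30%, B 2/20 = 10%.
- Limited to two scores: A 6/18 = 33.3%, B 2/6 = 33.3%.
- Share scored twice: A 18/20 = 90%, B 6/20 = 30%.

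**Does less re-evaluation always look better?** No.
- r = 30%, p = 50% gives 15%, against 27% for r = 90%, p = 30%. The centre with the worse true rate looks better.
- r = 60%, p = 60% gives 36%, against the same 27%. Here the centre that re-evaluates less looks worse, because its true rate is much higher.

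**If worsening patients are re-evaluated more often.** Assume a true rate of 30%, with re-evaluation of 90% of those who worsen and 30% of those who do not.
- Worsened and scored twice: 0.90 × 0.30 = 0.27. Not worsened and scored twice: 0.30 × 0.70 = 0.21.
- As written: 27%. Limited to two scores: 0.27 / (0.27 + 0.21) = 56%.

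In this case the restricted denominator is further from 30% than the literal one.

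**The case against.** The strongest reply has four parts.

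**The protocol never says that a missing re-evaluation counts as no increase.** That is correct; a reader might infer such a rule, but it is only the arithmetic effect of the two stated parts of the fraction. F16 keeps patients without re-evaluation identifiable, and a statistical analysis plan that is not shown could say how to treat them. The mention of reference data in the definition could also be read as limiting the indicator to patients with comparable scores. The denominator is nevertheless written out in the protocol without that limit, while the neighbouring indicator has one.

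**The indicator is diluted, not reversed.** This stands. A reader might infer that it runs opposite to quality, or that the centre re-evaluating least always looks best. At a given re-evaluation rate it still rises with the true rate, and the 36% against 27% example shows that the ordering can go the other way.

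**Restricting the denominator can bias upward.** This also stands, as the 56% example shows. It is why the restricted rate should not be reported alone.

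**The practical reach is limited.** This is one of 29 indicators. Objective 1 is descriptive, section 3.1 asks each centre to compare with itself, no between-centre test of this indicator is specified, and regression is reserved for indicators with extensive data in a sample of about 130 records. An effect on the determinants is therefore speculative. Some comparative reading remains, because section 8 highlights the highest and lowest results.

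On the pain tool, section F has no field naming the scale behind F15 and F17, although the indicator requires a valid one. A reader might infer that scores from different scales will be compared; nothing shows that they will, only that it could not be detected.

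**Conclusion.** The point holds as a dilution of Indicator 21 by incomplete scoring. It arises from a denominator that the protocol itself fixes, not from detail left to a later plan. If re-evaluation is unrelated to change, the reported value is the true rate multiplied by the share of patients scored twice. At the lowest share assumed, 20%, it is one fifth of the true rate, and it is 0% where nobody is re-evaluated. The re-evaluation and increase rates are assumptions throughout. The advantage to a centre that re-evaluates less holds when true rates are similar and can be overridden when they differ widely. It is worth correcting before results are reported, but it concerns one descriptive indicator and does not threaten the study as a whole.

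**What to change.** Redefine the Indicator 21 denominator as patients with shoulder pain who have both F15 and F17 recorded, in line with Indicator 20. For each centre, report side by side the number with shoulder pain, the number with two scores and the number with an increase. Do not read the increase rate as performance where the share scored twice is low or differs clearly between centres. Optionally, add one field to Appendix 2 for the pain tool, so that both scores can be confirmed to come from the same valid scale.

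The cost is one reworded line and, if adopted, one extra field; F14 to F17 are already collected. The denominator becomes smaller and the estimate less precise. The restricted rate can also be too high if worsening patients are re-evaluated more often, so the three counts must be shown together and not replaced by a single percentage.

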Proportion of post-stroke patients with a record that includes a therapeutic nursing plan (TNP), an individualized intervention plan (IIP) or a care plan (CP)

Numerator: Number of post-stroke patients with a record that includes a therapeutic nursing plan (TNP), an individualized intervention plan (IIP) or a care plan (CP)

Denominator: Total number of post-stroke patients

Indicator 25

Transfer at discharge: Proportion of post-stroke patients transferred at discharge to inpatient rehabilitation, outpatient rehabilitation, return to residence, long-term care centre or palliative care (Result by patient's place of transfer)

Numerator: Number of post-stroke patients transferred to inpatient rehabilitation, outpatient rehabilitation, return to residence, long-term care center or palliative care

Denominator: Total number of post-stroke patients discharged from hospital

Indicator 26

Proportion of post-stroke patients referred at discharge to a secondary prevention program (Specify type of referral)

Numerator: Number of post-stroke patients referred at discharge to a secondary prevention program

Denominator: Total number of post-stroke patients discharged

Reactivity

Indicator 27

Proportion of post-stroke patients and caregivers met by the team to discuss management of the patient and his or her needs following discharge

Numerator: Number of post-stroke patients and caregivers met by the team to discuss management of the patient and his or her needs following discharge

Denominator: Total number of post-stroke patients discharged

Indicator 28

Proportion of post-stroke patients and caregivers instructed prior to discharge on the following stroke-related topics of interest: modifiable risk factors, warning signs and symptoms of stroke, how to activate medical emergency services, post-discharge services available, prescribed medications and community resources

Numerator: Number of post-stroke patients and caregivers instructed prior to discharge on these topics of interest

Denominator: Total number of post-stroke patients

Indicator 29

Proportion of post-stroke patients and caregivers who were invited to participate in advance planning of care or had a documented conversation with a health professional regarding resuscitation and level of care

Numerator: Number of post-stroke patients who were invited to participate in advance planning of care or had a documented conversation with a health professional regarding resuscitation and level of care

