H17. Therapeutic nursing plan developed by nurse with patient and caregivers  1-No  2-Yes  3- Not applicable  99-Missing data	
H18. Beneficiary assistant work plan developed by nurse	

 1-No	 2-Yes	 3- Not applicable	 99-Missing data
H19. Patient's walking program developed by nurse or interdisciplinary team			
 1-No	 2-Yes	 3- Not applicable	 99-Missing data
H20. Transfer at discharge			
 1-Return to place of residence	 2- Outpatient rehabilitation services		
 3- Inpatient rehabilitation	 4- Long-term care center		
 5- Palliative care	 6-Not applicable		
 7- Other: _____			
H21. Referral regarding secondary prevention			
 1-No	 2-Yes	 3-Not applicable	 99-Missing data
H22. Clinician who referred to secondary prevention services			
 1-Nurse	 2-Neurologist	 3-Other: _____	
 99-Missing data			
H23. Readmission within 30 days for stroke-related issue			
 1-No	 2-Yes	 3-Not applicable	 99-Missing data

I. Discharge education

I1. Information on modifiable risk factors			
 1-No	 2-yes	 3-Not applicable	 99-Missing data
I2. Information on stroke symptoms			
 1-No	 2-Yes	 3-Not applicable	 99-Missing data
I3. Information on the urgency of consulting in the presence of stroke symptoms			
 1-No	 2-Yes	 3-Not applicable	 99-Missing data
I4. Information on post-stroke follow-up			
 1-No	 2-Yes	 3-Not applicable	 99-Missing data
I5. Information on prescribed medications			

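### Indicator 22 divides by patients already re-hospitalized, so it is not a readmission proportion and cannot be built from the collection sheet; a lesser mismatch affects Indicator 20

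*Protocol*

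**What the plan says.** Appendix 1, under Effectiveness, defines Indicator 22 in three lines:

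- Title: "Proportion of patients readmitted to short-term hospital care for a stroke-related issue after discharge (post 30 days" (the bracket closes there).
- The line giving the count on top: "Numerator: Number of patients readmitted to short-term hospital care for a stroke-related issue within 30 days after discharge".
- The line giving the base below it: "Denominator: Total number of post-stroke patients re-hospitalized after discharge".

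The data come from Appendix 2, where the single readmission item is "H23. Readmission within 30 days for stroke-related issue", answered No, Yes, Not applicable or Missing. No item records a re-hospitalization for any other reason or at any later time.

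Three nearby indicators that also start from discharge use a different base. Indicator 25 has "Denominator: Total number of post-stroke patients discharged from hospital", and Indicators 26 and 27 likewise divide by patients discharged.

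Indicator 20, in the same block, is titled "Proportion of patients with severe disability at discharge (mRS 0-3" (bracket closing after the range). Its count line is "Numerator: Number of patients with a modified Rankin score (mRS) between 0 and 3 at discharge", and its side instruction is "Calculate proportion of patients for each modified Rankin score, mRS of 1 to 5". Appendix 2 collects the raw discharge score in H9.

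Section 3.5 uses proportions to describe each centre and the three together, and to show which indicators meet the guidelines.

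**The concern.** A readmission proportion asks how many of the patients who left hospital came back. Indicator 22 instead starts from those who came back and asks how many of them returned early for a stroke-related reason. That answers a different question, and the value need not rise when readmissions rise. The time window is also in doubt, because the title points to the period after day 30 while the numerator and H23 count the first 30 days.

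The stake is the reported value of a performance indicator under Objective 1. Section 1 treats a quality indicator as a reliable and valid measurement, and Section 8.1 offers the study's method to other organizations, which would copy the definition as printed. For Indicator 20 the stake is smaller: a headline percentage whose name, score range and score list do not match.

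**Working it through.** The protocol states no readmission or disability figure, so there is nothing to reproduce. The check compares definitions and then applies simple ratios.

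**Indicator 22**

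1. Let D be the patients discharged alive, R those re-hospitalized after discharge for any reason, and x those with H23 = Yes. The title describes x/D; the definition gives x/R.
2. Which of these can be collected? x comes from H23. D comes from H1 and H2 (death and its date) with H3 and H4 (discharge and its date). R has no item in Appendix 2, so x/R cannot be computed from the planned data.
3. If the analyst follows the definition with the only readmission item available, R becomes x. The result is x/x = 100% for any x of 1 or more, and 0/0 for x = 0, where the proportion over D would be 0%.
4. Illustration. Section 3.3.2 plans about 130 records. Assume 10% die in hospital, so D = 130 × 0.90 = 117. The values of x are also assumed.

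| x (H23 = Yes) | H23 used for both parts | x/D |
|---|---|---|
| 0 | 0/0 | 0/117 = 0% |
| 4 | 4/4 = 100% | 4/117 = 3.4% |
| 8 | 8/8 = 100% | 8/117 = 6.8% |
| 16 | 16/16 = 100% | 16/117 = 13.7% |

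5. Sensitivity. With in-hospital deaths of 5% to 15%, D is about 124 to 110. For x = 8, x/D runs from 8/124 = 6.5% to 8/110 = 7.3%, and the H23-only reading stays at 100%.
6. Time window. The numerator and H23 agree on the first 30 days; the title's bracket is the only line that differs.

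**Indicator 20**

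1. The numerator counts scores 0, 1, 2 and 3. The per-score instruction lists 1, 2, 3, 4 and 5. Score 0 is in the first and missing from the second, which is visible without knowing the scale.
2. The label says severe disability. The protocol does not state which end of the scale is worse. On the scale's usual direction (higher is worse, an assumption here), 0 to 3 is the less disabled end.
3. Illustration with an assumed distribution per 100 patients of 10, 20, 15, 20, 25 and 10 for scores 0 to 5. The printed indicator is 10 + 20 + 15 + 20 = 65%, and scores 4 and 5 make up 25 + 10 = 35%. The listed scores 1 to 5 add to 90%, short of 100% by the 10% at score 0. H9 holds every score, so nothing is lost.

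**The case against.** The strongest reply is that the practical harm is small. H23 has one answer per patient, so an analyst who simply tabulates it obtains something close to the intended proportion, whatever Appendix 1 says. That stands, and it is why the correction is cheap. But it requires departing from the written definition and leaves the base to whoever does the tabulation.

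Appendix 1 also uses restricted bases elsewhere: patients screened (Indicator 10), with shoulder pain (21) and prescribed medication (23). So Indicators 25 to 27 alone do not prove that patients discharged was the intended base. This too is fair. The case rests on Indicator 22's own title and on the missing item. The groups in Indicators 10 and 21 are identifiable from E22 and F14; the group in Indicator 22 is not identifiable from any item.

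A reader might infer more: that the written ratio inflates readmission by a known factor D/R, or puts the centres in the wrong order. The algebra is correct, but any figure for it needs R, which the plan does not collect and the documents do not give. Such examples are hypothetical. Nor is a ranking planned. Section 3.1 says each centre compares with itself, and hypothesis 2 in Section 2 speaks only of similarities or differences between centre types.

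For Indicator 20, the objection that the scale's direction is not in the protocol is right. Calling the headline the opposite of its label therefore rests on an assumption. The mismatch over score 0 does not.

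Finally, Section 3.1 describes transfers between participating centres, and records run up to ethics approval. What counts as discharge, and whether 30 days could be observed, therefore needs stating with any corrected base.

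**Conclusion.** Indicator 22 is wrong as written. Its base turns it into a share of re-hospitalizations, that base cannot be formed from Appendix 2, and its title contradicts the time window in its numerator and in H23. If H23 serves for both parts, the value is 100% or undefined and says nothing about how often patients return. This conclusion needs no assumed rate; the percentages above only illustrate it. No size of distortion can be given for the written ratio itself, because the count it needs is not collected.

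Indicator 20 is a minor inconsistency between label, range and score list, with the values recoverable from H9. Two of 29 descriptive indicators are affected. Sample size and power do not depend on either.

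**What to change.** **Indicator 22.** Use one denominator: patients discharged alive from the index stay, taken from H1 and H3/H4, with the death date in H2 separating deaths before discharge from later ones. The numerator is H23 = Yes. Do not switch between this base and H23 Yes + No, which drops missing and not-applicable answers. Report those two counts beside the result; with m missing answers the proportion lies between x/D and (x + m)/D. Change the title's window to within 30 days. Add a sentence saying how transfers between centres and discharges with under 30 days of observable follow-up are handled.

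**Indicator 20.** Make name and range agree, either by renaming the indicator to describe scores 0 to 3 or by changing the range to fit the present name, and state the direction of the scale. Add score 0 to the per-score list.

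**Cost.** Wording changes to two definitions in Appendix 1. H1 to H4, H9 and H23 already exist, so no new data field is needed.
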